After screening and enrollment, the expanded cohort of subjects will be treated with radiation, temozolomide, and TTField therapy for 6 weeks akin to the safety lead-ins. The primary endpoint of treatment related adverse event (TRAE) rate and severity will be recorded and graded based on the NCI Common Terminology Criteria for Adverse Events (CTCAE) version 5.0 and DLT as defined in this protocol. The CTCAE v5.0 criteria can be found at:

https://ctep.cancer.gov/protocoldevelopment/electronic_applications/docs/CTCAE_v5_Quick_Reference_5x7.pdf Building on the already published long term safety data of combining TTField therapy with adjuvant TMZ after radiation therapy, this phase I study aims to assess the safety and tolerability of the device when used with concurrent radiation and TMZ at the initial postoperative or postbiopsy setting. Thus, the toxicity window for the primary endpoints of this study will start when subjects begin combined trimodal therapy (TTFields, RT, and TMZ) and end 8 weeks after completion of the trimodal therapy. After this time, TRAEs and DLTs are not monitored as part of the study endpoints because long term safety of adjuvant TTFields along with TMZ after radiation has been established in the preceding EF-14 trial. After completion of the DLT window, we will analyze and report on the safety and tolerability of combining TTField therapy with radiation and temozolomide prior to adjuvant therapy. We will report on those findings as well as preliminary survival trends that were observed after final completion of the study.

During the initial trimodal therapy phase, all subjects will receive weekly skin exams along with repeat neurologic exams at Day 22 and Day 43 while chemoradiation is underway. After completion of initial chemoradiation, they will have a 4-week hiatus from TMZ chemotherapy but will continue TTField therapy. After the hiatus, an MRI will be performed and TMZ will then be resumed for a minimum of 6 cycles of adjuvant therapy (along with continued TTField therapy for up to 2 years as tolerated) with appropriate laboratory monitoring per the standard of care.

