Two weeks after trimodal therapy, patients will receive a skin exam, scalp assessment and neurologic exam at Day 64 and will also be monitored at 4 weeks (Day 1 of Cycle 1 of adjuvant TMZ) and 8 weeks (Day 1 of Cycle 2 of adjuvant TMZ) after trimodal therapy to assess for post treatment toxicity that may be delayed. After conclusion of the DLT window, the treatment of

patients will be carried out per the standard of care in addition to continued TTFields therapy, as outlined in the clinical trial-related procedures section. The trial will then follow the clinical outcomes including duration of TTF use, completion of 6 cycles of temozolomide, and progression free survival at 6 months, and median overall survival and overall survival at 2 years.

Primary Study Endpoints

- Rate of treatment-related adverse events (TRAЕ)
- Rate of treatment-related severe adverse events (TRSAЕ)
- Rate of Dose-limiting toxicity (DLT)

Given that the primary objective of this study is to determine the safety and tolerability of adding TTField therapy to combined chemoradiation, our primary endpoints are related to safety as follows: Identify the rate of treatment-related adverse events as well as the rate of any severe adverse events during the combined treatment period and up to 8 weeks afterwards. For the same time frame, we will also document and assess the rate of dose-limiting toxicities. Safety of combined adjuvant treatment with TTFields and TMZ chemotherapy outside of the initial radiation is not a primary objective and will not be formally assessed in this study. The above endpoints will be assessed initially in the interim safety analyses involving the safety lead-in cohorts and then also in the main expanded cohort for the final analysis. See statistical methods for further details of the planned analysis. For any skin toxicity grade II or greater, we will also investigate and document, if apparent, whether this was related to the adhesive vs the ceramic disc component of the device.

Secondary Study Endpoints

- PFS6
- Overall survival (median OS and rate of OS at 2 years)
- Objective response by modified RANO criteria
- Median duration of TTFields use and rate of TTF compliance

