In the event of a dose-limiting toxicity, the subject will be discontinued from treatment and followed for toxicity assessment and management and a joint decision will be made by the investigator and sponsor whether to adjust the dose or schedule for other subjects or permanently close the study for safety. In the event that more than 33% of subjects experience a DLT, the study cannot continue unless a modification is made to the level of the particular treatment to which that adverse event is definitely attributable. As preliminary safety stops, the study will include two safety lead-ins receiving TTFields with concurrent chemoradiation. These initial 6 and then 15 subjects will undergo interim analyses after completion of chemoradiation to determine if the expanded cohorts should be permitted enrollment as planned or if a dose reduction in TTFields of 50% of the scheduled use is warranted for safety.

Subjects will continue to receive study treatment until confirmed tumor progression, unacceptable toxicity, or other discontinuation criteria as described; subjects MUST discontinue investigational product (and non-investigational product at the discretion of the investigator) if they meet criteria for removal from study therapy as referenced in that section.

Toxicity related to TTFields treatment: Treatment-related adverse events (TRAEs) and severe treatment-related adverse events (STRAEs) will be assessed in the following ways.

- Patients will be evaluated by a neuro-oncologist or radiation oncologist for potential skin toxicity from TTFields therapy. Routine skin care recommendations will be provided, including use clobetasol cream prior to electrode placement and adjusting array placement to avoid continued site irritation. If there are concerns by investigator, the subject will be referred to a dermatologist for specialized evaluation. Neurological and general physical evaluations as well as laboratory assessments will also be conducted by a neuro-oncologist or radiation oncologist to identify other potential toxicities.
- In addition to clinic visits and interventions, Patients will also be supported by a technician from Novocure for device troubleshooting and compliance checks.
- All other adverse effects, either mild, or serious, will be triaged by a physician in coordination with the primary investigators of the study.

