8. STATISTICAL CONSIDERATIONS

Interim analyses of the first and second safety lead-in cohorts will be performed using data collected from the beginning of the study to eight weeks following trimodal therapy for each patient. Patient characteristics will be summarized using means, standard deviations, medians, interquartile ranges, counts, or percentages, as appropriate. Primary endpoints will be summarized using counts and percentages of patients who experienced a treatment-related adverse event, treatment-related serious adverse event, or DLT for safety and stopping rules.

In the second interim analysis, the percentage of patients with inconclusive MGMT methylation status will also be summarized. Patients with inconclusive MGMT methylation status will be removed from the final study analysis, so we will use this percentage to assess the number of additional patients that need to be recruited to meet our sample size requirement of 30 patients. For example, if 2 out of 15 patients have an inconclusive MGMT methylation status at this stage, we will recruit 4 additional patients to meet the sample size requirement.

Using the intention-to-treat approach, the final analyses will be performed on all patients having received at least one day of use from the study device. Patients with an inconclusive MGMT methylation status will be excluded. Patient characteristics will be summarized using

means, standard deviations, medians, interquartile ranges, counts, or percentages, as appropriate.

Primary endpoints will be summarized using counts and percentages of patients who experienced a treatment-related adverse event, treatment-related serious adverse event, or DLT will be reported overall and by event type following trimodal treatment and 8 weeks thereafter to capture any later appearing toxicities. A subgroup evaluation by MGMT methylation status (methylated vs unmethylated) will also be performed.

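### Section 6 makes treatment-related severe adverse events a primary endpoint, but Section 8 summarises serious events and gives no summary by grade

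*Combined protocol and SAP*

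**What the plan says.** Section 6, Primary Study Endpoints, lists as its second item "Rate of treatment-related severe adverse events". The text below the list keeps the same adjective: "Identify the rate of treatment-related adverse events as well as the rate of any severe adverse events during the combined treatment period". Section 6, Safety Lead-ins, brings severity into the primary endpoint: "The primary endpoint of treatment related adverse event (TRAE) rate and severity will be recorded and graded", using CTCAE v5.0. Section 7a repeats the term under another abbreviation: "Treatment-related adverse events (TRAEs) and severe treatment-related adverse events (STRAEs) will be assessed in the following ways".

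Section 8 changes the word. For the interim analyses it counts patients with a "treatment-related serious adverse event, or DLT for safety and stopping rules". For the final analysis it states that patients with a "treatment-related adverse event, treatment-related serious adverse event, or DLT will be reported overall and by event type". Event type appears only in the final summary, and grade appears in neither.

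The Power Calculation in Section 8 takes severe skin irritation as its endpoint, with 30 patients, an expected rate of 5%, and 95% limits of 2% and 21%.

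**The concern.** Severe skin irritation is the added harm that the protocol expects from concurrent treatment, and it is the quantity used to justify 30 patients. A statistician who programs Section 8 as written would produce a serious-event rate where Section 6 promises a severe-event rate. No table would be required to show how many patients had severe skin toxicity. At the interims the planned summary has no event-type breakdown either.

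The primary analysis is descriptive, so no test or error rate is at risk. What is at stake is whether the report answers the listed primary question, and whether two analysts reading the plan would count the same patients.

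**Working it through.** The mismatch is textual, so the passages are set side by side. The one figure in Section 8 that concerns severity is reproduced first.

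**1. The plan's figure.** The inputs are n = 30 and an expected rate of 5% (Section 8, Power Calculation). The expected count is 30 × 0.05 = 1.5 patients. Rounded up to 2, p = 2/30 = 0.0667. With z = 1.96, the Wilson limits are

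(p + z²/2n ± z√(p(1−p)/n + z²/4n²)) / (1 + z²/n) = (0.1307 ± 0.1099) / 1.1281 = 0.0185 and 0.2132.

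This matches the stated 2% and 21%. At exactly 1.5/30 the Wilson limits would be 1.2% and 19.1%. The figure confirms that the precision statement concerns a severity rate. It does not measure how often severe and serious disagree.

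**2. Endpoint against summary.**

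| Place | Event named | Grade used |
|---|---|---|
| Section 6, Primary Study Endpoints, list | related, severe | not stated |
| Section 6, Primary Study Endpoints, text | severe (relatedness not repeated) | not stated |
| Section 6, Safety Lead-ins | related, rate and severity | CTCAE v5.0 |
| Section 7a | related, severe | CTCAE v5.0 |
| Section 8, interims | related, serious | none |
| Section 8, final | related, serious | none |

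**3. Are the two words interchangeable here?** Section 7, Definitions of Adverse Events, defines serious by a list of outcomes (such as death, threat to life or hospital admission), plus a clause that lets medical judgement make other important events serious. Severity is graded by CTCAE v5.0. The label severe is attached to Grade 3 only in the Section 7 scale for events that CTCAE does not list. The sets overlap, but each can hold patients that the other lacks:

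- A related Grade 3 skin reaction with no listed outcome, and not judged medically important, is severe and not serious.
- A related Grade 2 event that leads to admission is serious and not severe.

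**4. Could another planned row supply the severe count?**

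- *DLT row.* Section 7a counts Grade 3–4 radiation skin changes only when they last more than 7 days without improving, and other non-haematologic toxicity only above Grade 3. The TTFields dose-modification text in Section 6 counts a case where TTFields cannot be resumed within a month and is discontinued. Section 6 also foresees Grade 3–4 skin toxicity during radiotherapy that is handled by a break followed by resumption. A Grade 3 reaction that settles on a break is therefore not clearly a DLT.
- *Treatment-related event row.* That patient appears here, but without a grade. As an illustration, Section 4 reports mild to moderate skin irritation in 43% and severe reactions in 2% of patients in EF-14. In 30 patients this is 30 × 0.43 = 12.9 against 30 × 0.02 = 0.6 (1.5 at the plan's 5%). If all grades are counted, an ungraded skin row cannot show the severe cases.

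**The case against.** The best reply is that this is a drafting slip with little consequence. Section 8 introduces both summaries as summaries of the primary endpoints, which points back to the Section 6 list. Section 7a is loose with the words elsewhere: "All other adverse effects, either mild, or serious, will be triaged by a physician" sets mild against serious. This makes a slip likely. It does not settle which event is meant, because the written-out endpoint says severe in Sections 6 and 7a and serious has its own definition in Section 7.

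A second reply concerns data. Section 7, Recording of an Adverse Event, requires every event of Grade 3 or above to be entered in the trial database. If the analysis drew only on those events, the final treatment-related row by event type would be close to a severe-event row already. But the same section also has attribution entered for all adverse events, and Section 6 lists the overall treatment-related rate as a separate endpoint. That reading is possible but not stated.

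A third reply concerns oversight. Section 7, Adverse Events Monitoring, already requires a written report on adverse events and DLTs to the Data Safety Monitoring Committee (DSMC) after the first 6 patients, with its approval needed before expansion. A reader might infer from Section 8 that the DSMC cannot see severe skin events. The documents do not support that. What stands is narrower: no grade breakdown is specified for that report, and the requirement is stated for the first 6 patients, not for the review at 15.

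**Conclusion.** The inconsistency is real and should be fixed before analysis. As written, one of three listed primary endpoints, and the severe skin irritation rate behind the precision statement, have no explicit planned summary at either interim or at the end.

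Three stronger conclusions do not follow.

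- The stopping rules are not weakened: the Section 6 thresholds (2 or more of 6, 5 or more of 15) count DLTs only.
- The severe-event rate is not lost, because events of Grade 3 and above are entered with their CTCAE grade.
- The reported rate cannot be said to be wrong by any given amount. The documents give no frequency of severe events that are not serious, or the reverse. The chance of seeing a severe skin case in 30 patients would not measure that disagreement.

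The conclusion rests on reading Section 8 literally and on the Section 7 definition of serious. It is a reporting gap in a descriptive analysis.

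**What to change.** In Section 8, for both interims and the final analysis:

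- Report the count and percentage of patients with a treatment-related severe adverse event as the primary-endpoint row. Define it once as CTCAE v5.0 Grade 3 or higher. Section 7, Evaluation of Safety, mentions modified criteria for haematologic events, so the definition should say which scale applies to them.
- Show severe skin toxicity separately, so that the rate behind the Power Calculation is reported.
- Keep treatment-related serious adverse events as a separate row.

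Use one term and one abbreviation for the severe endpoint in Section 6 (Primary Study Endpoints), Section 7a and Section 8. In the explanatory text of Section 6, state whether severe events are limited to treatment-related ones.

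The cost is wording in three places and two further rows per analysis. No new data are needed, because entry of Grade 3 and above is already required. A table of all treatment-related events by each patient's highest grade would serve the severity part of the endpoint, but should be added only if the sponsor confirms that non-skin events of Grade 1–2 are entered: the explicit entry rule starts at Grade 3. Skin grades are already documented at the skin examinations (Appendix 3, note N).

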6. DESIGN OF THE CLINICAL TRIAL

Schema

General Study Design

This is a dual institution open-label, single arm, 3 stage, phase I trial of a medical device (TTFields) in newly diagnosed glioblastoma after maximal safe resection with the primary objective of determining safety.

Radiation dosimetry and mask modeling

Prior to the start of the study, a radiation dosimetry assessment and trial mask production will be performed. This serves as a preliminary safety and quality check. Using a phantom with a TTFields array in place on a medical linear accelerator, we will model the dosimetric impact of having the TTFields electrodes on the scalp at the time of RT delivery, as well as impact on the device operation. There may also be a small amount of scatter that may draw out dose superficially and cause increased skin toxicity. However, whether this would result in increased graded toxicity from routine use of TTFields therapy is unclear.

In the process of radiation planning, CT simulation involves production of a high-quality immobilization mask and acquisition of a non-contrast head CT from which to overlay the treatment maps for precise targeted radiation delivery. The presence of the scalp electrodes is expected to have minimal impact on the production of an immobilization mask, as the position of the electrodes would most likely not change from day to day. The immobilization setup can readily accommodate patients with long and dense hair, and will be able to accommodate the thin electrode pads on a shaved head. We perform daily image guidance with cone-beam CT for setup adjustment, so we can compensate for small variations in daily patient position in the mask. Finally, the presence of the electrodes may introduce image signal artifact in the planning CT scan. Prior to the study, we will analyze CT scans acquired on the phantom model for evidence of artifact and measure the signal to noise ratio and the change, if any, on Hounsfield units of normal tissues and structures imaged.

Safety Lead-ins

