7. SUBJECT ASSESSMENTS FOR SAFETY AND EFFICACY

The study procedure calendar for this study is provided in **Appendix 3**.

a) Evaluation of Safety and Tolerability**Dose Limiting Toxicity**

Dose limiting toxicities (DLTs) are defined as any severe or life-threatening treatment-related toxicity that precludes the use of a specified dose of any of the study treatments (TTFields, temozolomide, radiation) including continued use of Optune TTFields device at the standard treatment levels and schedule set out by prior studies. This study will prioritize preserving the standard of care for glioblastoma using approved dosing and radiation of temozolomide and radiation.

Toxicities will be graded according to the CTCAE (Version 5.0) scale. If multiple toxicities are seen, the presence of DLT should be based on the most severe toxicity experienced. Dose-limiting toxicities will be defined as any of the following events which occur during the experimental trimodal therapy with TTFields is added concurrently to radiation and temozolomide therapy or during the 8 weeks after RT is completed, and are considered by the investigator to be attributable to TTFields or the combination of TTFields with radiation and/or temozolomide:

- Any Grade > 3 thrombocytopenia, and Grade 4 anemia and neutropenia.
- Any nonhematologic Grade > 3 toxicity (including nausea, vomiting, or diarrhea), excluding alopecia.

- Any Grade 3-4 radiation-induced skin changes that persist for greater than 7 days and does not improve with management recommendations as outlined in toxicity management.
- Any adverse effect deemed by the investigator, patient's primary neuro-oncologist, or radiation oncologist to be life threatening in nature.

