prevent one of the outcomes listed in this definition. Examples of such medical events include allergic bronchospasm requiring intensive treatment in an emergency room or at home, blood dyscrasias or convulsions that do not result in inpatient hospitalization, or the development of drug dependency or drug abuse.

Life-threatening

An adverse event or suspected adverse reaction is considered *life-threatening* if, in the view of either the investigator or sponsor, its occurrence places the patient or subject at immediate risk of death. It does not include an adverse event or suspected adverse reaction that, had it occurred in a more severe form, might have caused death.

Recording of an Adverse Event

All grade 3 and above adverse events will be entered into the CTMS, Velos, whether or not the event is believed to be associated with use of the study device. Data about these events and their severity will be recorded using the NCI CTCAE v5.0.

All SAEs will be reviewed by a DSMC, which will consist of a panel of experts in oncology, neuro-oncology, biostatistics, or radiation oncology who are not direct investigators in this study. The PI will identify members of the DSMC and receive feedback and recommendations from the DSMC as to the safety of continuing the trial. The PI and study manager will be responsible for facilitating the proceedings as non-committee members. The committee will meet twice a year, or more if needed.

The Investigator will assess all adverse events, assign attribution of the possible association of the event with use of the investigational device, and this information will be entered into CTMS (Velos) using the classification system listed below:

Relationship	Attribution	Description
Unrelated to investigational drug/intervention	Unrelated	The AE is clearly NOT related to the intervention
	Unlikely	The AE is doubtfully related to the intervention
Related to investigational drug/intervention	Possible	The AE may be related to the intervention
	Probable	The AE is likely related to the intervention
	Definite	The AE is clearly related to the intervention

A more detailed definition of possible attributions is denoted in the following table:

Unrelated:	The event is clearly related to an event that may be due to environmental or accidental occurrence or other factors such as the subject's clinical state, therapeutic interventions, or concomitant drugs administered to the subject.
------------	--

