Unlikely	The event is most likely produced by other factors such as the subject's clinical condition, therapeutic interventions, or concomitant drugs administered to the subject, and does not follow a known response pattern to the study drug or device.
Possible	The event follows a reasonable temporal sequence from the time of drug administration or use of device, and/or follows a known response pattern to the study drug or device, but could have been produced by other factors such as the subject's clinical condition, therapeutic interventions, or concomitant drugs administered to the subject.
Probable	The event follows a reasonable temporal sequence from the time of drug administration or use of device, and follows a known response pattern to the study drug or device, and cannot be reasonably explained by other factors such as the subject's clinical condition, therapeutic interventions, or concomitant drugs administered to the subject.
Definite	The event follows a reasonable temporal sequence from the time of drug administration or use of device, and follows a known response pattern to the study drug or device, and cannot be reasonably explained by other factors such as the subject's clinical condition, therapeutic interventions, or concomitant drugs administered to the subject, and either occurs immediately following study drug administration or use of device or improves on stopping the study drug or device, or reappears on repeat exposure

The relationship of the adverse event to the study treatment must be specified using the following definitions:

Signs or symptoms reported as adverse events will be graded and recorded by the Investigator according to the CTCAE. When specific adverse events are not listed in the CTCAE they will be graded by the Investigator as *none*, *mild*, *moderate* or *severe* according to the following grades and definitions:

- Grade 0 No AE (or within normal limits)
- Grade 1 Mild; asymptomatic or mild symptoms; clinical or diagnostic observations only; intervention not indicated
- Grade 2 Moderate; minimal, local, or noninvasive intervention (e.g., packing, cautery) indicated; limiting age-appropriate instrumental activities of daily living (ADL)
- Grade 3: Severe or medically significant but not immediately life-threatening; hospitalization or prolongation of hospitalization indicated; disabling; limiting self-care ADL
- Grade 4: Life-threatening consequences; urgent intervention indicated
- Grade 5: Death related to AE

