Kaplan Meier survival analyses will be used to analyze the following secondary endpoints: 1) progression-free survival at 6 months and 2 years, 2) median time-to-death and overall survival at 2 years and 3) duration of TTF use. Log rank tests may be used in Kaplan Meier analyses to test for differences in survival curves amongst known prognostic factors such as age, duration and compliance of TTF use, KPS, extent of resection, IDH mutation status, and MGMT methylation status. The objective response by modified RANO criteria will be summarized with counts and percentages following trimodal treatment and at 2 years. The rate of TTFields compliance will be reported as the percentage of patients who used TTFields at least 75% of the minimum recommended usage of 18 hours a day on average, as assessed monthly.

The intention-to-treat analyses may be supplemented by per-protocol analyses, if the percentage of patients who did not follow standard of care recommendations as outlined for adjuvant and maintenance therapy following trimodal treatment is high.

Power Calculation

As we are expecting that patients will be more susceptible to skin irritation with concurrent therapy than with successive therapy, we focus on severe skin irritation as our endpoint for this power calculation. We expect 5% of patients will experience severe skin irritation based on a 2% rate in the Stupp et al. 2015 study (EF-14)²⁴ which used TTField therapy following initial chemoradiation treatment. Assuming a sample size of 30 patients of whom 5% experience severe skin irritation, we can say with 95% confidence that the true percentage of patients with severe skin irritation is no lower than 2% and no higher than 21% based on a one-sample binomial proportion. Outside of severe skin toxicity, the rate of any adverse event is not expected to differ significantly from that established by the EF-14 trial.

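### Section 8 summarises only treatment-related events and DLTs, so the severe-event rate that Section 6 names without an attribution limit would not be reported

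*Combined protocol and SAP*

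**What the plan says.** Section 8 bases the two interim analyses on counts and percentages of patients with a "treatment-related adverse event, treatment-related serious adverse event, or DLT for safety and stopping rules". The final analysis uses the same categories: after treatment-related events it goes on, "treatment-related serious adverse event, or DLT will be reported overall and by event type following trimodal treatment", with follow-up to 8 weeks afterwards.

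All three categories pass through the investigator's judgment. Section 7 (Recording of an Adverse Event) states: "The Investigator will assess all adverse events, assign attribution of the possible association of the event with use of the investigational device". For DLTs, Section 7 requires events to be "considered by the investigator to be attributable to TTFields or the combination of TTFields with radiation and/or temozolomide". Section 6 describes the design: "This is a dual institution open-label, single arm, 3 stage, phase I trial of a medical device".

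Data capture is wider than the tables. Section 7 states: "All grade 3 and above adverse events will be entered into the CTMS, Velos, whether or not the event is believed to be associated"; the association meant is with the device.

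Section 6 (Primary Study Endpoints) words the severe-event endpoint in two ways. The bullet restricts it to treatment-related severe events. The paragraph below pairs the treatment-related event rate with a severe-event rate that carries no attribution qualifier, for the combined treatment period and up to 8 weeks after it.

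**The concern.** The section that specifies the analysis is narrower than the endpoint text it serves. If the Section 6 paragraph means what it says, part of a primary endpoint has no planned summary. If it does not, the documents still carry three descriptions of one endpoint, and whoever writes the tables has to choose among them after the data are seen.

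Attribution also bears more weight here than in a controlled trial. With no concurrent arm, nothing in the data would show that events had been wrongly assigned to tumor or to radiation. The primary hypothesis in the synopsis concerns the safety profile as a whole, and a table filtered by attribution cannot describe that by itself.

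**Working it through.** The only calculation in Section 8 is the interval for severe skin irritation (n = 30, 5% assumed, 2% to 21%). It is not in dispute, and it reproduces as a Wilson interval with 5% of 30 = 1.5 rounded up to 2 events. With p = 2/30 = 0.0667 and z = 1.96:

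(p + z²/2n ± z√[p(1−p)/n + z²/4n²]) / (1 + z²/n) = (0.1307 ± 0.1099) / 1.1280 = 1.85% to 21.3%.

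The point itself turns on the text. Side by side:

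| Place | Severity term | Attribution limit |
|---|---|---|
| Section 6, endpoint bullet | severe | treatment-related |
| Section 6, paragraph below the bullets | severe | none stated |
| Section 8, interim and final | serious | treatment-related |
| Section 7, database entry rule | Grade 3 and above | none |

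1. Severe and serious are different concepts in this protocol. Section 7 ties severe to Grade 3 on its grading scale. It defines serious by outcome: death, threat to life, hospitalization, incapacity, birth defect or an important medical event. A Grade 3 event need not be serious, and a serious event need not be Grade 3. So Section 8 does not explicitly list even the treatment-related severe rate in the Section 6 bullet. DLT has its own criteria and does not stand in for it.

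2. For Grade 3+ events in a given window, patients with a related event are a subset of patients with any event. The difference is the number of patients whose Grade 3+ events were all judged unrelated. Section 8 reports neither the total nor that difference.

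3. Compare the expected effects under Treatment Modalities in Section 6. Headache, fatigue and seizure appear for both TTFields and radiation. Necrosis, memory impairment and altered cognition appear for radiation only. An event of the second kind is easier to judge unrelated to the device. The example is softer for cognition, because Section 4 reports that mild confusion was more frequent with TTFields in EF-14.

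4. Precision of an all-cause table, using exact (Clopper-Pearson) limits: lower = 0.025 quantile of Beta(x, n−x+1), upper = 0.975 quantile of Beta(x+1, n−x). The rates are assumptions, since the documents give none. At n = 30:
   - 9/30 (30%): 14.7% to 49.4%
   - 15/30 (50%): 31.3% to 68.7%
   - 21/30 (70%): 50.6% to 85.3%

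   At the lead-ins the intervals are wider. With no events, the upper limit is 1 − 0.025^(1/6) = 45.9% for 6 patients and 1 − 0.025^(1/15) = 21.8% for 15. The table would be descriptive. It changes no sample size, error rate or stopping rule.

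**The case against.** Treatment-related events and DLTs are the declared phase I endpoints, and other parts of the protocol look beyond them. The DSMC reviews all serious events, the report on the first 6 patients covers adverse events without a related-only limit, and death from any cause enters the Kaplan-Meier analysis of overall survival. These are real safeguards, but none supplies an all-cause Grade 3+ or serious-event summary. The first is monitoring, the second is described only for the first lead-in, and the third covers death alone.

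The term treatment-related is also ambiguous. Treatment Modalities uses it for radiation and temozolomide effects, so an event blamed on either might still be tabulated. Section 7 points to device attribution. The possibility of missing events depends on the device reading.

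An all-cause rate in 30 patients without a control cannot isolate harm from TTFields either. That is correct, and it is why the two tables belong together.

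Three stronger readings are tempting, and the documents do not support them:

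- A reader might infer that the attribution scale pushes neurological events out of the tables, because the definition of Unlikely opens with "The event is most likely produced by other factors such as the subject's clinical condition, therapeutic interventions, or concomitant drugs administered to the subject". That definition also requires that the event not fit a known response pattern of the study drug or device. Seizure, headache and fatigue are listed as expected TTFields effects, so they fit Possible, which counts as related.
- A reader might infer that a planned comparison with EF-14 fails, from the sentence that, severe skin toxicity aside, "the rate of any adverse event is not expected to differ significantly from that established by the EF-14 trial". This is a design expectation, with no test, margin or EF-14 overall rate. A Grade 3+ table would not give an any-grade rate in any case.
- A reader might put a figure on the loss by assuming an all-cause rate and a share judged related. Neither input is in the documents, so the result would only reflect the choice of inputs.

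**Conclusion.** The point holds in a limited form. Section 8 contains no all-cause summary of Grade 3+ or serious events, and following it exactly would not report the severe-event rate in the Section 6 paragraph. The conclusion assumes that the missing qualifier in that paragraph is deliberate. If the treatment-related limit was meant to carry over, the conflict between severe and serious remains and still needs settling. That some events would be absent from the tables is a possibility, not a demonstrated bias, and its size is unknown. The declared related-event and DLT endpoints remain usable. The change is worth making because the gap touches a primary endpoint and is cheap to close.

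**What to change.** Reconcile the bullet and paragraph in Section 6 with Section 8: state whether the endpoint is severe, serious or both, and whether it is limited by attribution. State too whether treatment-related means related to the device or to any study treatment.

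In Section 8, for both lead-in analyses and the final analysis, add the number and percentage of patients with any Grade 3+ adverse event, any serious adverse event, and death, regardless of attribution. Break these down by event type over the DLT window, give exact 95% intervals, and place them beside the treatment-related table.

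The cost is one extra table and a few sentences. The Grade 3+ data are already to be entered in the database, and no stopping or treatment rule changes. The drawback is that all-cause rates will include disease events and the background toxicity of radiation and temozolomide, so neither table should be shown without the other.
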